Despite the success of the above studies in selected populations of patients with chronic NGB, once changes in the neurological control of the bladder have occurred following SCI they are mostly irreversible. In chronic NGB, treatments must be directed at the local muscle level in order to control the high bladder pressures, incontinence and other symptoms. Consequently, the majority of research into the effects of spinal cord injury on the urinary bladder has focused on patients with well-established chronic neurogenic bladder physiology.

Interventions during the acute phase of SCI aimed at preventing the development of, or reducing the symptoms of NGB, remain an understudied area of research.

Purpose and Objectives

AIM 1: To determine the effect of sacral neuromodulation on urodynamic parameters following acute spinal cord injury. The following outcomes will be evaluated by urodynamic assessment at one year post-SCI: (1) maximum cystometric capacity, (2) bladder compliance, (3) presence of detrusor overactivity, and (4) volume and pressure for first detrusor contraction.

AIM 2: To assess the impact of sacral neuromodulation on patient-reported quality of life after acute spinal cord injury. Patient-reported QoL will be assessed using the SCI-QOL bladder question bank and bladder/voiding diaries (Appendix B). Mean SCI-QOL score, daily number of catheterizations, average catheterization volume, and episodes of incontinence per day will be compared between groups at one year post-SCI.

AIM 3: To examine the impact of sacral neuromodulation on quantifiable clinical outcomes. Patients will be followed longitudinally during the study period and assessed for the following: (1) need for anti-cholinergic medications and/or onabotulinum toxin A treatment, (2) number of symptomatic UTIs per year, (3) complications attributable to the device, (4) need for revision of device or leads due to lead migration or failure, (5) development of hydronephrosis.

Study Population

Age of Participants: 18+

Sample Size:

At Utah: 20
All Centers: 60

Inclusion Criteria:

Inclusion Criteria
Age > 18 years
Ability to implant device less than 12 weeks post-SCI
Presence of acute SCI at or above T12
ASIA Scale A or B
Expectation to perform CIC personally or have caretaker perform CIC

Exclusion Criteria:

Exclusion Criteria

Inability to perform CIC

Pre-existing SCI

Pre-existing progressive neurological disorder

Autonomic dysreflexia

Prior sacral back surgery

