
NOTE: Implantation is usually accomplished via a two-step process involving a placement of the permanent quadripolar electrode alongside the S3 nerve root under local or general anesthesia. This permanent lead is controlled by a temporary external programming device for 7-14 days. If greater than 50% improvement in clinical symptoms over that test period, the IPG is implanted subcutaneously under during a second surgical procedure. Because the study hypothesis dictates early stimulation of the sacral nerve roots with a primary outcome evaluated one year post implant, the quadripolar electrical lead and IPG will be placed in the same procedure. This will avoid delay in stimulation of the sacral nerves during the critical window for preventing adverse neuroplastic changes. Patients will be mostly insensate due to their SCI or being under general anesthesia for the procedure. Therefore, to confirm intraoperative placement we will rely upon expected motor responses (anal bellows and toe flexion). If correct motor responses cannot be elicited intraoperatively than the patients will not undergo implantation and will be included in the randomized arm

but in an ‘intention-to-treat’ manner.

FDA approved programming parameters for the Interstim II system will be utilized in this study as follows. The device will provide continuous stimulation (i.e. always on) without discrete treatment periods. The PrimeAdvanced Surescan IPG is capable of generating a maximum voltage of 10.5 volts, 2 volts higher than the Interstim II system, however, it will be programmed to function within the normal Interstim II system parameters (maximum 8.5 volts). Additionally, it will be programmed to use the same stimulation pulsewidth (210 msec) and frequency (14Hz) as the Interstim II system. The area under the stimulation curve will be the same or less than intended by the Interstim II parameters.

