Each patient will be evaluated intraoperatively as is standard clinical practice to select stimulation parameters that result in typical, consistent physiological responses (e.g. anal bellows and first toe rotation). The default 14 Hz frequency will be maintained. The electrode with the lowest amplitude stimulation as a proxy for the most closely placed electrode to the S3 nerve. This electrode be trialed first. The stimulation amplitude will be set at 0.7V per protocol as was utilized in the one prior bilateral SNM study in acute SCI. Note: If the subject has S3 sensation (incomplete SCI), the amplitude will be set 0.1V lower than the level of sensation. In such sensate patients, each lead will be programmed individually and then both leads will be activated simultaneously to determine whether further amplitude reduction is needed. These parameters will be set during the initial programming session and will remain constant for the duration of the study. All study centers will utilize the same protocol.

Standardized demographic data based on the National Institutes of Neurological Disorders and Stroke (NINDS) Common Data Elements (CDEs) will be collected via patient interview and evaluation of the electronic medical record including mechanism of SCI and medical comorbidities. All measured outcomes are listed in Table 1 by Aim. At enrollment, all participants will complete the following: (1) standardized 3-day voiding diary to annotate the catheterization time, amount and time of fluid intake, and incontinence events, (2) 24 hour pad weight test, (3) 3-day bowel diary to quantify baseline bowel habits; (4) inventory of current medications; and (5) the SCI-QOL questionnaires (Appendix B). (6) 24 hour pad weight test averaged over 3 days. Repeat measurements will be obtained during clinic visits at 3, 6, 9, and 12 months after enrollment. (7) All participants will undergo baseline urodynamic testing at enrollment. For patients randomized to the intervention arm, urodynamic testing will be completed less than 2 weeks before implantation of the device. Urodynamic testing will be repeated at 3 months and then again at 12 months.

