At each time point, a retrospective review since the prior time point will be performed in order to capture major events such as hospitalizations, additional surgery or death as well as additional subjective data. Those additional subjective data will include: (1) current usage of anti-cholinergic medications and/or onabotulinum toxin A treatment (2) number of culture proven symptomatic UTIs per year (3) complications attributable to the device, (4) need for revision of device or leads.

A renal ultrasound will be obtained at the end of 12 months to evaluate for the development of hydronephrosis. This will be compared with baseline CT or US imaging obtained during their initial trauma evaluation.

There will be a video available for participants to view for additional information.

Procedures performed for research purposes only:
Implantation of sacral neuromodulator and leads

Statistical Methods, Data Analysis and Interpretation

Sample size calculations for this study were based on a mean maximum cystometric capacity of 220.7 mL (SD=103.3), as reported by Sievert et al 60, and a feasibility of enrolling 30 patients per arm within the study period. After accounting for a 15% loss to follow-up we expect 25 evaluable patients per arm. To achieve 80% power at a 5% significance level with 25 patients per arm (N=50), we can detect an effect size of a 38% treatment effect (84 mL increase in capacity). This calculation was simulated for a two-tailed t-test incorporating one interim and one final look at the data using the O'Brien and Fleming (OBF) method and running 50000 simulations (using PASS v. 11.0.8 software). An interim analysis will be conducted at 50% enrollment (N=26 after loss to followup, 13 patients per arm) accrual, and the decision to stop early will be governed by an OBF significance level of 0.003. A 0.051 significance level will be used to evaluate the final analysis. The DSMB's decision to stop early will be guided both by interim results and clinical judgment, especially in the context of emerging, relevant literature.

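### Does tying the interim look to 50% enrollment leave it with too few one-year outcomes for its N=26 and its 0.003 level?

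*Combined protocol and SAP*

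**What the plan says.** The section Statistical Methods, Data Analysis and Interpretation plans a "two-tailed t-test incorporating one interim and one final look at the data". It times the first look as follows: "An interim analysis will be conducted at 50% enrollment (N=26 after loss to followup, 13 patients per arm) accrual". It adds that "the decision to stop early will be governed by an OBF significance level of 0.003". Shortly before, the same section applies 15% loss to follow-up to 30 enrolled per arm and expects 25 evaluable per arm, 50 in all.

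The outcome comes late. The implantation note under Study Procedures justifies placing lead and generator in one operation "with a primary outcome evaluated one year post implant". Aim 1 under Purpose and Objectives says "The following outcomes will be evaluated by urodynamic assessment at one year post-SCI". The visit schedule under Study Procedures, which counts clinic visits from enrollment, says "Urodynamic testing will be repeated at 3 months and then again at 12 months".

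No section gives a data cut for the interim, an accrual rate, or a statement on whether enrollment continues while outcomes mature.

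**The concern.** The interim sentence puts two different quantities together. The trigger is a count of patients enrolled (30 of 60). The figure in brackets is a count of patients with an outcome. With a one-year outcome, the two cannot coincide on the same day unless enrollment has paused.

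If the look were taken on the day the 30th patient enrolled, the only planned interim would be spent on a small part of the primary data, or on none. The 0.003 level would also be out of place. An O'Brien-Fleming-type level depends on the fraction of outcome information, and 0.003 belongs to about one half. At stake would be an interim with almost no chance of detecting the planned effect, and a boundary that does not match its information.

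**Working it through.** **Inputs from the documents.** 60 enrolled, 30 per arm; 15% loss; 50 evaluable; interim N 26 (13 per arm); interim level 0.003; two-sided overall level 5%; planned difference 84 mL; SD 103.3 mL; one-year outcome. **Assumption.** Accrual duration A is not given, so uniform accrual over A = 24, 36, 48 or 96 months is shown.

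**1. The plan's interim figures.**
- First half of the cohort after loss: 30 × 0.85 = 25.5, stated as 26. Per arm: 15 × 0.85 = 12.75, stated as 13.
- Information fraction: 26/50 = 0.52, or 25/50 = 0.50.
- Two-sided O'Brien-Fleming-type spending: 4 × [1 − Φ(2.2414/√t)]. At t = 0.50 this is 4 × [1 − Φ(3.170)] = 0.00305. At t = 0.52 it is 4 × [1 − Φ(3.108)] = 0.0038.

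So 26 and 0.003 agree with each other if the first 30 patients have been followed for one year. At 26 of 50, 0.003 is slightly strict.

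**2. The literal reading.** Evaluable outcomes at the 30th enrollment = 30 × max(0, (A/2 − 12)/(A/2)) × 0.85. Enrolled when the first 30 reach 12 months = min(60, 60 × (A/2 + 12)/A).

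| Accrual (months) | Evaluable at 30th enrollment | Fraction of 50 | Enrolled when first 30 reach 12 months |
|---|---|---|---|
| 24 | 0 | 0 | 60 |
| 36 | 8.5 | 0.17 | 50 |
| 48 | 12.75 | 0.255 | 45 |
| 96 | 19.1 | 0.38 | 37.5 |

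None of these reaches 26, so the literal reading contradicts the N in its own sentence.

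**3. Chance of crossing 0.003 if 84 mL is true** (noncentral t, SD 103.3):
- 4 per arm: 1.5%
- 6 per arm: 3.3%
- 9 per arm: 7.1%
- 10 per arm: 8.7%
- the stated 13 per arm: 14.0%

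**4. Overall type I error when 0.003 is used too early.** Bivariate normal, correlation √t, with a final level of 0.049 (the level that brings the total to 0.05 at half information):
- t = 0.17: 0.0513
- t = 0.255: 0.0509
- t = 0.38: 0.0504
- t = 0.50: 0.0500

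The largest rise is 0.0513 − 0.0500 = 0.0013. A bound that needs no accrual assumption treats the two looks as independent: 1 − 0.997 × 0.951 = 0.0519, a rise of at most 0.0019. With no outcomes, no test is possible and no error is spent.

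The plan states 0.051 for the final look. That figure alone gives 0.0520 at half information. It is a separate matter, unrelated to when the look is taken, and is not counted here.

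**The case for a change.** The strongest case for a change is that an interim trigger should need no inference. The operative word is enrollment, and a data manager or the DSMB could act on it. Timing settled after data have accumulated also invites the question whether the data drove it. The calculations behind this case are correct, and it is true that the documents give no data cut. The 3-month urodynamics do not rescue the literal reading: they are not the primary time point, and at the 30th enrollment they would still give only about 13 to 23 evaluable patients for accrual of 12 to 60 months.

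A second point also stands. The start of the one-year clock varies: Aim 1 counts from injury, the implantation note from implant, and the visit schedule from enrollment. If the clock starts at injury and enrollment falls near week 12, the lag is about 9.25 months. The counts at the 30th enrollment then become about 5.8, 12.4, 15.7 and 20.6 instead of 0, 8.5, 12.75 and 19.1. These are still below 26, so the anchor changes the size of the gap but not the reading.

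What does not stand is the step from loose wording to harm. Nobody can have a count after loss to follow-up on the day the last of those patients enrolls. Anyone preparing the look would find far fewer than 13 per arm, see that the stated N was not met, and wait. A look taken too early would also be very unlikely to stop the trial, and it would leave the final test, the sample size and the estimate as planned.

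**Conclusion.** The concern describes a real looseness in the wording but not a fault in the design. The stated 26 patients and the 0.003 level fit each other and fit one reading: the first half of the cohort, followed to the one-year assessment, less 15%. Analysts would fill the missing data cut that way.

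The misreading costs little. With a 12-month lag and uniform accrual over 24 to 96 months, overall type I error moves by at most about 0.0013, and under any accrual pattern by no more than 0.0019. The chance of an early stop under the planned effect falls from 14% to between 0% and about 9%, so what is lost is part of an already small chance.

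Rewriting the trigger would gain little. It would mainly put the evident intent into words. Recomputing the boundary by a spending function would move the interim level only from 0.003 to 0.0038 at 26 of 50. Under the same accrual assumptions, by the time the first 30 patients reach 12 months about 38 to 60 of the 60 are already enrolled, so a correctly timed look spares few or no enrollments. The accrual duration is assumed throughout. The conclusion does not depend on it, because no duration in the range makes the literal reading agree with the plan's own N.

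### The final test at 0.051 exceeds the stated two-sided 5% level; with the 0.003 interim look kept, the matching final level is about 0.049

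*Combined protocol and SAP*

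**What the plan says.** All the relevant statements are in the section Statistical Methods, Data Analysis and Interpretation.

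- Level and power: "To achieve 80% power at a 5% significance level with 25 patients per arm (N=50"), for a detectable difference of 84 mL with an SD of 103.3 mL.
- Test and looks: the calculation was "simulated for a two-tailed t-test incorporating one interim and one final look at the data", by the O'Brien-Fleming method, "running 50000 simulations (using PASS v. 11.0.8 software").
- Interim timing: half of enrolment, given as "N=26 after loss to followup, 13 patients per arm".
- Interim level: "the decision to stop early will be governed by an OBF significance level of 0.003".
- Final level: "A 0.051 significance level will be used to evaluate the final analysis".

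The section names no spending function, gives no futility boundary and does not explain where 0.051 comes from. It adds that the DSMB will weigh clinical judgment as well as the interim results.

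**The concern.** In a group-sequential design that holds 5% overall, the interim efficacy look uses part of the 5%, so the final test must be run below 0.05. Here the final level is above 0.05, although an interim look is also planned. A final p-value of 0.0505 would be declared significant in a trial described as controlling error at 5%. At stake is the threshold for the comparison on which the trial is sized, and whether the type I error claim can be defended when the result is reported.

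**Working it through.** **Inputs**, all from the statistical section: two-sided 5% level; one interim and one final look; interim level 0.003; final level 0.051; 13 per arm at the interim and 25 per arm at the end, so the information fraction is t = 26/50 = 0.52 (nominally 0.50); difference 84 mL; SD 103.3 mL.

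**1. The plan's power figure.** The standard error of the difference is 103.3 × √(2/25) = 29.22 mL, and the noncentrality is 84/29.22 = 2.875. A single two-sided t-test at 0.05 on 48 df then has power 80.4%. With both looks as written (0.003, then 0.051) it is 80.8%. The stated 80% reproduces.

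**2. Lower bound on the error, without modelling.** If the interim never stops the trial, the final test alone rejects a true null 5.1% of the time. Stopping for efficacy can only add rejections. The overall error is therefore at least 5.1% unless a binding futility rule removes some, and none is stated.

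**3. Overall error with both looks.** Overall error = 1 − P(|Z1| < z1, |Z2| < z2), where Z1 and Z2 are bivariate normal with correlation √t. The critical values are z1 = 2.968 for 0.003, and z2 = 1.951 for 0.051 or 1.969 for 0.049.

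| Levels (interim / final) | t = 0.50 | t = 0.52 | t-tests at 13, then 25 per arm |
|---|---|---|---|
| 0.003 / 0.051 | 0.0520 | 0.0519 | 0.0521 |
| 0.003 / 0.049 | 0.0500 | 0.0499 | 0.0501 |

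The last column adds simulated interim-only rejections (10 million null trials) to the exact final level.

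**4. Rounding.** Let the printed levels stand for anything in 0.0025–0.0035 (interim) and 0.0505–0.0515 (final). The overall error then runs from 0.0512 to 0.0527, so rounding does not explain the excess.

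**5. The matching final level.** Fix the interim at 0.003 and solve for 5% overall. The final level is 0.0490 at t = 0.50, 0.0491 at t = 0.52 and about 0.0489 for the t-tests. If 0.003 is itself rounded (0.0025 to 0.0035), the normal-theory solution lies between 0.0488 and 0.0493.

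**6. Comparison with O'Brien-Fleming forms.**

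| Form | t = 0.50 | t = 0.52 |
|---|---|---|
| Classical (critical values C/√t and C) | 0.0052 / 0.0480 | 0.0060 / 0.0477 |
| Spending function 4 × (1 − Φ(2.241/√t)), with 2.241 the upper 1.25% normal point | 0.00305 / 0.0490 | 0.0038 / 0.0488 |

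Neither form gives a final level above 0.05. The spending form at t = 0.50 gives an interim level that rounds to the plan's 0.003, and its partner is 0.049.

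**7. Practical effect of moving from 0.051 to 0.049.**

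- Two-look power at 84 mL: 80.8% to 80.3%.
- Observed difference needed at the final look, t(48 df) × 29.22: 2.0016 × 29.22 = 58.5 mL against 2.0198 × 29.22 = 59.0 mL.
- Chance that the final p-value falls between 0.049 and 0.051: 0.2% under the null, 0.5% at 84 mL.

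**The case against.** Four points can be made for leaving the text alone.

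- **The 5.2% assumes that the boundary is followed.** The DSMB may use judgment. If crossing 0.003 did not lead to stopping and significance were judged only at the end, the error would be 5.1%, and stopping early for other reasons would lower it further. This is fair as to size: 5.1% to 5.2% describes the range when no other stopping occurs. It does not rescue the threshold, because discretionary stopping is not a binding rule and cannot be credited with controlling error.
- **The origin of 0.051 is unknown.** With 50,000 simulations, the Monte Carlo standard error of a 5% rate is √(0.05 × 0.95/50,000) = 0.00097. A simulated overall error of 0.051 would be about one standard error from 0.05. The figure may be such an output reported in the wrong place, or a typing error for 0.049; the documents settle neither. Under either explanation the sentence is wrong, because it prescribes 0.051 as the operating level. What stands is that 0.049 is right only if 0.003 is the intended interim level.
- **The effect is almost nil**, in a trial labelled Phase I. This is true and is why the point is minor. The plan nevertheless states a formal level, a power and a stopping boundary, and these should agree.
- **The 5% covers one comparison only.** The plan lists several urodynamic, quality-of-life and clinical outcomes, and this section gives no multiplicity rule. The error rates here concern maximum cystometric capacity alone, which limits their scope but does not alter the inconsistency.

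**Conclusion.** The concern holds and is minor. No binding futility rule or other text offsets a final level of 0.051, so the threshold as written does not hold the stated level. The excess is about 0.2 percentage points when only the efficacy boundary acts, and at least 0.1 point if the interim never stops the trial and no other early stopping occurs. That the level is exceeded does not depend on which O'Brien-Fleming form was meant. The replacement value does: 0.049 rests on keeping 0.003 at about half information. The plan's power statement and sample size are unaffected.

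**What to change.** Confirm from the sponsor's own boundary output that 0.003 is the intended interim level. If it is, keep it, replace 0.051 with 0.049 for the final analysis, and name the boundary or spending function so that the pair can be traced. If the classical O'Brien-Fleming form is intended, change both levels together, to about 0.005 and 0.048 at half information. Make the change before the final analysis.

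With 0.003 kept, the cost is one number in the statistical section and about 0.5 percentage points of power (80.8% to 80.3%). No extra patients are needed, and the statement of 80% power for 84 mL can stay.
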